# Statistical Analysis Plan (SAP)

## 7 STATISTICAL CONSIDERATIONS AND ANALYSIS

### 7.1 Derived variables

Details for deriving efficacy variables are discussed in [Sections 4.1, 4.2](#), and [4.3](#). The below set of variables are the basic demographic variables and some general variables.

Variables	Formula
Age at informed consent (in years)	year of informed consent – year of birth
Body mass index (BMI;kg/m  )	weight (kg)/[height (m)] 
Extension Study day at any visit	(visit date – date of first IMP administration in the extension study) + 1 for visit dates on or after first IMP dosing date in the extension study; (visit date – date of first IMP administration in the extension study) for visit dates before first IMP dosing date in the extension study
Parent Study day at any visit	(visit date – date of first IMP administration in the parent study) +1 for visit dates on or after first IMP dosing date in the parent study; (visit date – date of first IMP administration in the parent study) for visit dates before first IMP dosing date in the parent study
Change from baseline	Post baseline value – Baseline
Percent change from baseline#	[(Post baseline value – Baseline)/Baseline]*100

#: If the baseline value of any component of ACR is equal to 0, the following algorithm will be used in evaluating the percent change from baseline: If change from baseline is also equal to 0, then percent change from baseline is set to be 0%; If change from baseline is > 0, then percent change from baseline is set to be 9999999%. Note: these conventions are only used when deriving ACR20/50/70 and will be described in the ACR listing. Such values will be flagged and explained in the footnote for presentation in the ACR listing.

### 7.2 Handling of missing data and outliers

#### 7.2.1 Missing data analysis methods

In general, missing values for any of efficacy and safety endpoints will not be imputed when summarizing these endpoints using descriptive statistics.

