### **9.3.5      Investigational Medicinal Product Discontinuation**

Subjects may voluntarily discontinue IMP for any reason at any time, or completely withdraw from the study (see [Section 9.3.4](#)). Subjects who consent will undergo the EoT/Follow-up assessment approximately 4 weeks after administration of the last dose of IMP.

At any time during this long-term extension study, subjects not deriving sufficient clinical benefit in the opinion of the Investigator should be discontinued from IMP. Investigators should monitor the clinical benefit of each subject in an ongoing manner throughout the study in order to make the determination as to whether it is appropriate for them to continue to participate.

IMP must be discontinued under the following circumstances and further steps need to be discussed with the medical monitor:

- A serious adverse event (SAE), drug reaction or complication, or an unacceptable AE, whether attributed to IMP or not, that precludes continuation of treatment with IMP. This includes the development of allergic reactions or the development of other potentially serious drug reactions to medication required by the protocol,
- Diagnosis of malignancy (except basal or squamous cell carcinoma) during study (treatment may be continued at the discretion of the subject and Investigator, and in consultation with the medical monitor),
- Subjects who develop suicidal behavior ([Section 12.4](#)),
- Evidence of pregnancy,
- Withdrawal of informed consent,
- Lost to follow-up,
- Significant non-compliance of the subject with study procedures,
- Decision of the Sponsor to terminate the subject, site, or the study.

The derivation of clinical response (at Week 52 for the Phase 2 parent study) will be made within the IVRS system using information provided by the study site. The IVRS system will determine the subject's eligibility to continue into the long-term extension study. Subjects who fail to meet eligibility criteria at the end of their parent study will not be eligible to continue to the long-term extension study in accordance with the IVRS instruction, and would continue in the Follow-up period of their parent study.

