### **12.3 Description of Statistical Analyses**

All the safety and efficacy data will be summarized descriptively through appropriate data tabulations and descriptive statistics. For continuous variables, unless otherwise stated, the number of available observations (n), mean, standard deviation (SD), median, and range will be provided. For categorical variables, the number and percentage in each category will be displayed.

The last value of a variable taken before the first dose of IMP in parent study will be used as the original Baseline value. The last value before the first dose of IMP in the long-term extension study will be used as the LTE Baseline value. Unless otherwise specified, missing or dropout data will not be imputed for the purpose of data analysis.

A more detailed description of study analyses will be presented in the Statistical Analysis Plan (SAP).

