# Statistical Analysis Plan (SAP)

non-missing components to determine whether the ACR endpoint is a response or non-response, then ACR endpoint is not missing, else if the available non-missing components are not sufficient to determine the response status of ACR endpoint then it is considered missing.

If the baseline value of any component is equal to 0, the following algorithm will be used in evaluating the percent change from baseline:

- If change from baseline is also equal to 0, then percent change from baseline is set to be 0%;
- If change from baseline is  $> 0$ , then percent change from baseline is set to be 9999999%.

These imputed percentages of 0% and 9999999% will be used to derive the ACR endpoints only.

Any ACR endpoint that utilizes these imputed values to achieve response will be flagged in by-subject listings.

In addition, any hsCRP value below the LLOQ will be reported as “<0.xxx” in database and will be set to the LLOQ and used in analyses.

HAQ-DI derivation is described in [Section 12.1.1](#)

SF-36 is derived per [Section 12.1.2](#)

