## 8.6 Efficacy analyses

Responder-type endpoints (ACR20, ACR50, ACR70) will be summarized with response rates and 95% confident intervals (CI) by treatment group and visit.

Observed and change from baseline in continuous endpoints (tender joint counts, swollen joint counts, PGA of disease activity, PtGA of disease activity, patient’s pain assessment, HAQ-DI, acute-phase hsCRP, ESR, SF-36) will be summarized by treatment group and visit with n, mean, SD, median, and range. No statistical tests will be performed.

At the start of the long-term extension study, each subject will continue to receive the same dose

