## Statistical Analysis Plan (SAP)

### 8.9 Interim analysis

An IA to review safety and efficacy data will be performed following the last subject's Week 52 visit or early termination prior to Week 52. Additional IAs (for safety and PK/ADA assessments only) may be performed as needed to support reporting requirements or as needed for internal decision-making. Details of the statistical methodology and operational processes for later IAs will be described in a separate document if different from those described here.

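### ACR20/50/70 rates before the open-label switch are observed-case rates; subjects who stop treatment leave the denominator, so response in the ASaT population tends to be overstated

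*SAP*

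**What the plan says.** **Missing data.** SAP section 7.2.1 says that, in general, "missing values for any of efficacy and safety endpoints will not be imputed when summarizing these endpoints using descriptive statistics". Protocol section 12.3 agrees: unless otherwise specified, "missing or dropout data will not be imputed for the purpose of data analysis". At endpoint level, SAP section 4.1 adds that "if the available non-missing components are not sufficient to determine the response status of ACR endpoint then it is considered missing"; it is not set to non-response.

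**Efficacy summaries.** SAP section 8.6: "Responder-type endpoints (ACR20, ACR50, ACR70) will be summarized with response rates and 95% confident intervals (CI) by treatment group and visit". It also says "No statistical tests will be performed". SAP section 6.1 makes the ASaT population (entered the extension and received at least one dose) primary for efficacy. Section 8.1 displays efficacy by nominal visit and leaves unscheduled assessments to the listings. Section 8.9: "An IA to review safety and efficacy data will be performed following the last subject's Week 52 visit", or early termination before it.

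**Who enters and who leaves.** Inclusion criterion 3 (Protocol section 9.3.1) requires ACR20 response at parent Week 52 plus benefit in the Investigator's opinion. Under Protocol section 9.3.5, "subjects not deriving sufficient clinical benefit in the opinion of the Investigator should be discontinued from IMP" at any time. Footnote c to the original-protocol schedule in SAP Table 1 gives anyone who withdraws from study drug one EoT/Follow-up visit, about 4 weeks after the last dose.

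**Scope.** SAP section 2.3 records that the amendment removed the efficacy objectives, and section 3.1 that no efficacy assessments follow the switch to open-label 100 mg every 12 weeks.

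**The concern.** A subject who stops study drug contributes ACR data up to withdrawal and possibly at EoT/Follow-up, then has no status at later scheduled visits. With no imputation and no stated denominator, the natural reading of section 8.6 is responders divided by subjects with a determinable status at that visit. That describes subjects still in the study and assessed, whereas section 6.1 names everyone who entered and was dosed.

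Lack of benefit is one reason for stopping, so the missing data are unlikely to be unrelated to response. The cohort was also selected as ACR20 responders at parent Week 52. A reader of the interim or the final report could take a high, stable rate as durability of response in all entrants when part of it reflects who remains. The confidence interval gives no protection, because it covers sampling error only.

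**Working it through.** The plan gives no expected response rate, dropout rate or power, so there is no figure to reproduce.

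**Inputs**
- N = 286, the maximum number of entrants (SAP section 3.1), used as an illustrative ASaT size. It pools the three groups, whereas the planned tables are by group.
- p, observed-case response rate at a visit: not given; assumed 80-90%.
- d, share of ASaT with no ACR status at a scheduled efficacy visit: not given; assumed 5-20%, all taken to be off study drug.

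**Formulas**
- Observed-case rate = p.
- Non-responder rate on ASaT = p × (1 − d).
- Excess = p − p(1 − d) = p × d. This is never negative, so the observed-case rate cannot be below the non-responder rate.
- More generally, if those missing respond at rate m, the ASaT rate is p(1 − d) + m × d and the excess is d × (p − m). Observed cases overstate whenever m is below p; p × d is the upper end, at m = 0.

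**Corners of the assumed range**
- 0.80 × 0.05 = 4.0 points
- 0.90 × 0.05 = 4.5 points
- 0.80 × 0.20 = 16 points
- 0.90 × 0.20 = 18 points

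**In whole subjects, N = 286**

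| Assumed p, d | Observed cases | Non-responder, ASaT | Excess (points) |
|---|---|---|---|
| 80%, 5% | 218/272 = 80.1% | 218/286 = 76.2% | 3.9 |
| 80%, 20% | 183/229 = 79.9% | 183/286 = 64.0% | 15.9 |
| 90%, 5% | 245/272 = 90.1% | 245/286 = 85.7% | 4.4 |
| 90%, 20% | 206/229 = 90.0% | 206/286 = 72.0% | 17.9 |

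In the second row the 95% Wilson interval is 74.2-84.6% for observed cases and 58.3-69.3% for the ASaT rate, so the reported interval would not reach the ASaT figure.

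**Sensitivity**
- If the missing respond at half the observed rate (m = 40% when p = 80%, d = 20%), the excess is 0.20 × (0.80 − 0.40) = 8 points.
- A lower observed rate, as is likely for ACR50 and ACR70, shrinks the excess in proportion: at p = 70%, d = 20%, 160/229 = 69.9% against 160/286 = 55.9%, or 13.9 points.

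**Entry selection** is a separate matter that changing the denominator does not touch. At most 286 of the 391 parent-study subjects (73.1%) can enter, all having met ACR20 at parent Week 52 apart from any protocol deviations.

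**The case against.** The strongest case against is that this is a residual, descriptive part of a safety extension. Protocol section 12.2.2 measures no efficacy endpoints, later interims cover safety and PK/ADA only (SAP section 8.9), and no tests are planned. Protocol and SAP agree openly on not imputing. Discontinuations with reasons are tabulated by group on ASaT (SAP section 8.3), so a reader could work out a rough bound. Counting every discontinuation as failure also goes too far the other way, since Protocol section 9.3.5 lists pregnancy, loss to follow-up and Sponsor decisions among the reasons. This last point stands: the non-responder rate is a conservative bound and should accompany the observed-case rate, not replace it.

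A reader might also infer more than the documents support:

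- **That four-year response is overstated.** ACR is assessed only before the open-label switch, so only those visits and the Week 52 interim are affected.
- **That failures are systematically removed, leaving a rate close to that among continuing responders.** The discontinuation rule rests on the Investigator's view of benefit, not on loss of ACR20; a subject may lose ACR20 and stay on drug, or the reverse. The rule is quoted from the amended protocol, and the original protocol, under which ACR was collected, is not available to confirm it applied throughout. Failures at visits before withdrawal are counted. EoT/Follow-up includes the ACR components and may record others, although it is the Week 208 column and no rule carries its result to the missed visits.
- **That the regimens cannot be compared.** No comparison is planned, and nothing shows that discontinuation differs by group.
- **That every ACR endpoint starts at 100%.** Entry requires ACR20 only.

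SAP section 7.2.1 is hedged and section 8.6 names no denominator, so observed cases is the natural reading, not an explicit statement.

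**Conclusion.** The point holds for ACR20/50/70 at visits before the open-label switch, including the Week 52 interim. As written, the SAP leads to rates that are conditional on remaining in the study and being assessed. They do not describe the ASaT population named for efficacy, and they tend to be too high for it. An observed-case rate is a legitimate conditional summary; the fault is that it stands alone.

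The size is not known. The 4 to 18 points rest wholly on assumed values for response and missingness and on treating all missing subjects as non-responders; the excess is smaller if some of them still respond. With safety as the amended objective, this is worth correcting but does not threaten the main conclusions of the study.

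**What to change.** In SAP sections 7.2.1 and 8.6:

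1. State the denominator of the observed-case ACR rates and show the number assessed at each visit.
2. Beside them, present a non-responder analysis on the ASaT denominator: subjects who discontinued study drug before a scheduled efficacy visit count as non-responders at that visit.
3. Treat visits not performed because efficacy assessments ended with the amendment as not scheduled, so that they are neither failures nor part of the denominator.
4. Label all ACR rates as conditional on ACR20 response at parent Week 52. This deals with entry selection, which the second analysis cannot correct.

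The cost is a short SAP revision and one extra set of descriptive tables. Displayed rates in the second set will be lower, and they form a conservative bound because discontinuations unrelated to efficacy also count as failures. No data collection or clinical rule changes.

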#### 7.2.2 Handling of missing or incomplete dates

Imputation rules for missing or partial AE start date are defined below:

If the start date has month and year but day is missing, the first day of the month will be imputed

- If this date is earlier than the first dose date, then the first dose date will be used instead.

# Statistical Analysis Plan (SAP)

- If this date is later than the AE stop date (possibly imputed), then the stop date will be used instead.

If the start date has year, but day and month are missing, the 1st of January will be imputed

- If this date is earlier than the first dose date, then the first dose date will be used instead.
- If this date is later than the AE stop date (possibly imputed), then the stop date will be used instead.

If the start date of an event is completely missing, then it is imputed with the first dose date.

Imputation rules for missing or partial AE stop date are defined below:

- If the stop date has month and year but day is missing, the last day of the month will be imputed
- If the stop date has year, but day and month are missing, the 31th of December will be imputed

After the imputation, the imputed dates will be compared against the date of death, if available. If the date is later than the date of death, the date of death will be used as the imputed date instead.

Imputation rules for missing or partial medication start/stop dates are defined below:

**Missing or partial medication start date:**

- If only Day is missing, use the first day of the month.
- If Day and Month are both missing, use the first day of the year.

**Missing or partial medication stop date:**

- If only Day is missing, use the last day of the month.
- If Day and Month are both missing, use the last day of the year.
- If Day, Month and year are all missing, assign ‘continuing’ status to stop date

# Statistical Analysis Plan (SAP)

## 8 STATISTICAL METHODS

### 8.1 General Statistical Conventions

All statistical procedures will be completed using SAS version 9.4 or higher.

Continuous variables will be summarized using descriptive statistics, including number of subjects (n), mean, median, standard deviation (SD), minimum and maximum. One additional decimal point for mean and median and 2 additional decimal points for SD will be used.

For categorical variables, summaries will include counts of subjects and percentages. Percentages will be rounded to one decimal place.

Two-sided 95% confidence intervals (CI) will be provided when relevant.

For summary purposes, baseline will be defined as the last available value prior to the date of first IMP administration in parent study.

For reporting purpose, summary tables for efficacy variables and safety variables will be displayed by nominal visit as appropriate. Unscheduled assessments will not be included in the summary tables, but will be in data listings.

All subject data, including those derived, will be presented in individual subject data listings. Unless otherwise stated, unscheduled visit results will be included in date/time chronological order, within patient listings only. All listings will be sorted by treatment group, subject number, date/time and visit. The treatment group as well as patient's sex and age will be stated on each listing. Unless otherwise stated, data listings will be based on ASaT population.

The treatment groups will be displayed in the format below in tables:

- 200 mg Tildrakizumab q4wk
- 200 mg Tildrakizumab q12wk
- 100 mg Tildrakizumab q12wk

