## 9.2 Discussion of Study Design

Subjects with PsA will be eligible for this long-term extension study if they have completed approximately 1 year of treatment in the parent study. At the time of the first subjects entering the long-term extension study, other subjects may still be continuing in the parent Phase 2 study.

The study has been developed based on design features used in the ongoing parent Phase 2 study for PsA subjects as well as ongoing Phase 3 studies for subjects with psoriasis. No efficacy endpoints will be assessed for the study.

The study has been designed to provide an immediate entry into the long-term phase from the end of the parent study with the last assessment from the parent study becoming the Baseline

assessment of the long-term extension. This enables scientific evaluation of safety at all measured time points beyond completion of treatment in the parent study and comparison back to the original Baseline of the parent study. Subjects who entered the wash-out phase of their parent study prior to study site activation of this long-term extension protocol will also be eligible for inclusion and will re-initiate the tildrakizumab dose last received in the parent study. The duration of time in the wash-out phase of the parent study prior to entry to the long-term extension is anticipated to be short, thus enabling continued efficacy assessment across the long-term extension study.

All safety measures are consistent with evaluations used in clinical studies and previous studies with tildrakizumab.

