# Statistical Analysis Plan (SAP)

## 1 INTRODUCTION

The purpose of this Statistical Analysis Plan (SAP) is to provide a detailed description of the statistical methods, data derivations and data presentations to be employed for study protocol CLR\_18\_07 “A Multiple-Dose, Long-Term Extension Study to Demonstrate the Safety and Efficacy of Tildrakizumab in Subjects with Psoriatic Arthritis and [REDACTED] or [REDACTED] [REDACTED] who have previously completed studies with Tildrakizumab” which was originally issued on 15 Mar 2018. The protocol was amended on 22 July 2020 with the title “A Long-Term Extension Study to Demonstrate Safety of Tildrakizumab in Subjects with Psoriatic Arthritis Who Have Previously Completed Study with Tildrakizumab”.

Any deviations from this SAP will be described in the Clinical Study Report (CSR).

This SAP supersedes the statistical considerations identified in Protocols for CLR\_18\_07 and where considerations are substantially different, they will be identified as such in this document.

This SAP has been developed and approved prior to a data snapshot and unblinding of the clinical database for Protocol CLR\_18\_07.

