## 8.7 Safety analyses

Safety analyses will be conducted on the ASaT population and will be performed for all safety variables specified below.

The subjects will be summarized based on the actual treatment received at the beginning of the extension study.

The safety analyses of changes from baseline to a specific time point in safety variables (e.g., laboratory parameters, vital signs, and ECG) will only include subjects from ASaT who have data available for both the baseline and the time point under consideration unless otherwise specified. Where relevant, temporal relationships to parent study baseline will be described.

No statistical tests will be performed.

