## 8.7.2 Clinical laboratory evaluations

For the purposes of summarization in both the tables and listings, all laboratory values will be presented in SI units. If a lab value is reported using a nonnumeric qualifier e.g., less than (<) a certain value, or greater than (>) a certain value, the given numeric value will be used in the summary statistics, ignoring the nonnumeric qualifier.

Clinical laboratory parameters observed values and changes from Baseline will be summarized at each scheduled visit. Unscheduled visits will not be included in the summary table, but will be displayed in the listings.

Values outside the normal range will be categorized as H (above the normal range) or L (below the normal range) based on the laboratory's reference range and these will be flagged in the listings of individual subject data.

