### 10      CHANGES TO PLANNED ANALYSIS FROM STUDY PROTOCOL

Not applicable.

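### SAP 8.1 defines only the parent-study baseline, so no planned table clearly shows paired change since extension Week 0; its rule on unscheduled assessments, read literally, also lets the C-SSRS worst-case table omit the worst score

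*SAP*

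**What the plan says.** Protocol 12.3 defines an original Baseline, taken before the first parent-study dose, and a second one: "The last value before the first dose of IMP in the long-term extension study will be used as the LTE Baseline value". It does not say which baseline any table uses. Protocol 9.2 describes the design as allowing "evaluation of safety at all measured time points beyond completion of treatment in the parent study and comparison back to the original Baseline".

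SAP 8.1 gives a single definition for summaries: "baseline will be defined as the last available value prior to the date of first IMP administration in parent study". SAP 7.1 defines change as the later value minus Baseline, without saying which baseline. The safety sections follow the same pattern. For laboratory data, SAP 8.7.2 says "Clinical laboratory parameters observed values and changes from Baseline will be summarized at each scheduled visit". SAP 8.7.3 and 8.7.5 do likewise for vital signs and ECG parameters. SAP 8.7.5 adds by-visit shift tables of ECG interpretation, and SAP 8.7.6 adds a C-SSRS table that crosses the baseline score with the worst score in the treatment period. SAP 8.7 also says "Where relevant, temporal relationships to parent study baseline will be described".

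On departures from the protocol, SAP 1 says that "where considerations are substantially different, they will be identified as such in this document". Section 10, "CHANGES TO PLANNED ANALYSIS FROM STUDY PROTOCOL", declares none.

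On unscheduled assessments, SAP 8.1 sends them to the listings and keeps them out of the summary tables. SAP 8.7.6 states no exception.

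**The concern.** Changes in vital signs, laboratory values, ECG and C-SSRS are primary safety objectives (Protocol 8.1, SAP 2.1), and the study exists to describe the extension period. A change or shift measured from before the parent study combines what happened in that study with what happened after Week 0. A table of this kind cannot separate a subject who worsened during the extension from one who worsened earlier and stayed the same. The protocol created a baseline that would separate them, but the SAP does not carry it over and does not mention its absence.

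The second issue concerns the C-SSRS table alone. A worst-case summary is read as including every score recorded. If unscheduled scores are left out, an assessment prompted by a clinical worry, which may well hold the worst score, is the one that does not count.

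**Working it through.** The plan gives no figure to reproduce. The check compares texts and adds some illustrative arithmetic.

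**1. Which baseline do the safety tables use?**
- Protocol 12.3 defines both baselines. SAP 8.1 defines one, the parent-study baseline.
- SAP 4.1 (for ACR) and 8.4.2 (baseline characteristics) also name the parent study.
- In SAP 3.1 and the schedule of assessments, extension Week 0 is labelled as the baseline visit, and SAP 3.3 counts 208 weeks from the Baseline assessment. These are visit labels and do not define an analysis reference.
- SAP 8.7 speaks of baseline and then separately of parent study baseline, which hints that the two might differ.

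No SAP section defines an extension baseline for analysis, so SAP 8.1 governs on the better reading. On the other reading, the term in 8.7 is undefined and conflicts with 8.1. The text needs correcting either way.

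**2. How much of the interval precedes the extension?** Extension Week 0 is parent Week 52 (Protocol 9.1.1). At extension week w, the share of the change interval before Week 0 is 52/(52+w). For a subject who spent the full 20-week wash-out before entry it is 72/(72+w). Protocol 9.2 expects shorter stays, so the second column is an upper bound.

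| Week | No wash-out | Full wash-out |
|---|---|---|
| 8 | 52/60 = 87% | 72/80 = 90% |
| 20 | 52/72 = 72% | 72/92 = 78% |
| 56 | 52/108 = 48% | 72/128 = 56% |
| 104 | 52/156 = 33% | 72/176 = 41% |
| 152 | 52/204 = 25% | 72/224 = 32% |
| 200 | 52/252 = 21% | 72/272 = 26% |

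These are shares of calendar time. They do not measure bias.

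**3. What does a shift table lose?** Take assumed ideation scores at parent baseline, Week 0 and an extension visit, with the last also the worst in the extension.
- With 3, 0, 3, the parent-baseline table shows 3 to 3, no shift. Against Week 0 it would show 0 to 3.
- With 0, 3, 3, the parent-baseline table shows 0 to 3. Against Week 0 it would show no shift.

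Neither Week 0 score involves a yes to C-SSRS question 4 or 5, the specific trigger in exclusion criterion 15, although the investigator's judgment could still exclude a subject.

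Counts by visit do not restore the pairing. Suppose n subjects have both values, a are abnormal at Week 0 and b later. The number newly abnormal can then lie anywhere from max(0, b − a) to min(b, n − a).

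**4. Unscheduled C-SSRS scores.** Table 9-1, footnote a, allows unscheduled safety assessments, and footnote k specifies the form that asks about the time since the last visit. Under the SAP 8.1 rule, read literally, an unscheduled score stays out of the worst-case table. If that assessment counts as the last visit, the next scheduled form need not capture the episode again; the documents do not settle this.

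**The case against.** The strongest reply is that the SAP removes no table that the protocol clearly required. Protocol 12.3 assigns neither baseline to a table, Protocol 12.3.1 also uses baseline without qualification, and Protocol 9.2 plans comparison with the original Baseline. That reference has a rationale: it is the only value before any study drug, whereas Week 0 is an on-treatment value in subjects selected for response. All of this stands. A reader might infer that the parent baseline is the wrong choice, or that the SAP plainly broke its promise in section 1. The documents support neither. The promise covers only substantial differences, and whether this is one can be argued.

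A reader might also infer that no safety table describes the extension on its own. That goes too far:
- treatment-emergent events are counted from extension consent (SAP 8.7.1);
- observed laboratory, vital-sign and ECG values are summarized by visit, so means can be compared with Week 0 unpaired;
- SAP 8.7.6 counts subjects with ideation or behavior at each assessment time, and the form covers the time since the last visit, so the extension ideation in the 3, 0, 3 example would appear there;
- SAP 8.1 promises listings of all subject data.

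On the second issue, it would be wrong to say the SAP is silent on unscheduled scores, because 8.1 states a rule. That rule can be read as aimed at the by-visit tables in the same paragraph, but 8.7.6 does not say so. Suicidal ideation and behavior events are also adverse events of clinical interest, tabulated and listed under SAP 8.7.1, which covers part of the gap.

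What remains is the missing definition, the missing paired view from Week 0, and a worst-case table under a rule that does not suit it.

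**Conclusion.** The point holds as a cheap improvement. The missing extension baseline is clear from the text. That the safety change and shift tables run from before the parent study is the better reading but not the only one, given the wording of SAP 8.7 and the Week 0 visit labels.

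The consequence is narrow. Paired individual change since Week 0 appears in no planned table, and the ECG-interpretation and C-SSRS shift tables are affected most. Mean changes in continuous variables can largely be worked out from observed values. The time shares assume that the parent baseline falls at about parent Week 0; a reader might take them for the size of an error, but they say nothing about how far values moved in either period. The number of subjects affected and the net direction cannot be determined from the documents. No statistical test is planned, and no conclusion is threatened.

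The C-SSRS point rests on a literal reading of SAP 8.1 and is partly mitigated by the adverse event tables and listings.

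**What to change.** 1. In SAP 8.1, define both baselines as in Protocol 12.3 and state which one each safety table uses.
2. Add shift tables of ECG interpretation and C-SSRS against the LTE Baseline, beside those from the parent baseline. If output allows, add change summaries for laboratory values, vital signs and ECG parameters. The shift tables come first because their pairing cannot be recovered from other tables.
3. In SAP 8.7.6, state that the worst-case score uses all assessments in the extension treatment period, including unscheduled ones. By-visit tables stay on scheduled visits.
4. Record any remaining difference from the protocol in SAP 10.

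Table 9-1 already collects laboratory, vital-sign, ECG and C-SSRS data at Week 0, so no new visit or measurement is needed. The cost is a few sentences in the SAP and more descriptive output.
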